##### **3.2.3 Exploratory Efficacy Endpoints**

- Change from baseline to Week 24 and from baseline to Week 48 in FVC (liters).
- Change from Day 1 to Week 48 in a panel of serum and plasma biomarkers that will be determined by FibroGen.
- Relationship between known chromosomal loci associated with IPF and the response to FG-3019.

## 4 STUDY DESIGN

### 4.1 Study Population

Male or female subjects, 40 to 80, years old who have IPF diagnosed in accordance with criteria published in the 2011 international consensus guidelines. Subjects who have failed or are intolerant of products approved for treating IPF are eligible.

### 4.2 Description of the Study

This is a Phase 2, randomized, double-blind, placebo-controlled multicenter study. Subjects who have failed or are intolerant of products approved for treating IPF are eligible. Other subjects must be fully informed of the potential benefits of approved products and make an informed decision that they prefer to participate in a clinical trial in which they may be randomized to placebo.

Subjects who sign informed consent will undergo screening visits to determine their eligibility. Eligible subjects will be stratified based on prior therapy with nintedanib and/or pirfenidone (yes/no) and randomized (1:1) to one of two treatment arms:

Arm A: FG-3019, 30 mg/kg

Arm B: Matching placebo

[figure not shown]
Approximately 60 centers in the United States and other countries will participate in this clinical trial.

#### 4.2.1 Study Periods

There are four study periods:

- Screening Period (up to 6 weeks)
- Randomized Treatment Period (48 weeks)
- Extended Treatment Period (sub-set of subjects [see definition above]; duration based on changes in FVC (Section 4.2.3))
- Follow-Up Period (all subjects will undergo a final safety assessment at 4 weeks after last dose of study drug.)

A schematic overview of the trial is provided in Figure 1.

**Figure 1. Study Schema**

#### 4.2.2 Randomized Treatment Phase

Treatment should begin within 42 days of the first screening visit. Study Drug (FG-3019 [30 mg/kg] or placebo) will be administered by IV infusion every 3 weeks for a total of 16 infusions over 48 weeks.

The schedule of assessments of safety and efficacy are provided in Appendix 1 and Appendix 2. Safety and tolerability will be monitored closely by FibroGen. Cumulative safety experience will be evaluated by FibroGen on a regular basis. Final efficacy assessment is in Week 48. Subjects who do not enter the Extended Treatment Phase will undergo end-of-study (EOS) assessment (Appendix 3) on Week 49 (4 weeks after last dose of study drug).

After all subjects complete Week 48 evaluations or prematurely discontinue the study, data will be cleaned and locked for the primary analysis of efficacy and safety.

#### 4.2.3 Extended Treatment Period (Weeks Identified with –EX Suffix)

At the time of roll over into the Extended Treatment Period, the study subject treatment assignment will be unblinded only to designated personnel not associated with the study at FibroGen Inc. To continue to maintain the study blind, the first dose for all subjects in the Extended Treatment Period will be administered over approximately 2 hours.

##### 4.2.3.1 Subjects Enrolled under the Original Protocol and Assigned to Arm A: FG-3019

All subjects in Arm A whose FVC percent predicted value shows less than 3% absolute decrease from baseline in the Randomized Treatment Period will be offered participation in an Extended Treatment Period. These subjects may continue treatment until FVC percent predicted decreases 3% or more on two consecutive scheduled evaluations compared to the original pre-treatment baseline.

#### **4.2.3.2 Subjects Enrolled Under Amendment 1 or Subsequent Amendments and Assigned to Arm A: FG-3019**

All subjects in Arm A whose FVC percent predicted value is greater than the original pre-treatment baseline in the Randomized Treatment Period will be offered participation in an Extended Treatment Period and may continue treatment until FVC percent predicted is equal to or less than the pre-treatment baseline on two consecutive scheduled evaluations.

#### **4.2.3.3 Subjects Enrolled Under the Original Protocol or Amendment 1 and Subsequent Amendments Assigned to Arm B: Placebo**

All subjects assigned to Placebo (Arm B) will be offered participation in the Extended Treatment Phase for 45 weeks. Placebo subjects in the extension study are treated identically to subjects randomized to FG-3019 in Amendment 1, except for the fact that the baseline for these patients is the time at which they are enrolled into the extension phase (Baseline for Placebo subjects is Week 48 value). Change in FVC percent predicted during the extended treatment phase will be compared to this new baseline. Those subjects whose FVC percent predicted value is either equal to or greater than the new baseline may continue treatment with FG-3019 until FVC percent predicted is equal to or less than the baseline on two consecutive scheduled evaluations. See Section 4.2.3 for details regarding the Extended Treatment Period.

### **4.2.4 End of Treatment and Follow-up**

#### **4.2.4.1 Randomized Treatment Phase**

- Subjects assigned to either FG-3019 or placebo who discontinue treatment before week 48 should undergo end of treatment and safety assessment visits (Appendix 3).
- Subjects who were assigned to FG-3019 complete 48 weeks of treatment and are not going on to the Extended Treatment Period should undergo a Safety Assessment visit (Appendix 3); Week 48 evaluation is identical to End of Treatment visit. Thus, subjects who complete Week 48 and are not eligible for the extension study only need the final safety assessment. Subjects who enter the Extended Treatment Period do not need a final safety assessment because they are continuing treatment).
- Subjects who were assigned to placebo who complete 48 weeks of treatment but do not enter the Extended Treatment Period should undergo a safety assessment as described in Appendix 3.

#### **4.2.5 Extended Treatment Phase**

- Subjects who were assigned to FG-3019 and continue in the Extended Treatment Period will undergo early termination and safety assessment visits (Appendix 3) at the time they discontinue treatment **unless** they discontinue treatment at Week 48 EX. In this case, they only undergo the safety assessment visit. This is applicable whether subjects stop before or after week 48 EX.
- Subjects who were assigned to placebo, and receive FG-3019 in the Extended Treatment Phase and then discontinue treatment at Week 48 of the Extended Treatment Period should undergo a Safety Assessment visit (Appendix 3).

- Subjects who were assigned to placebo, and receive FG-3019 in the Extended Treatment Phase who discontinue treatment prior to Week 48 of the extended treatment period will undergo early termination and safety assessment visits (Appendix 3) at the time they discontinue treatment.

#### **4.2.6 Placebo Control Group**

In order to evaluate the effect of treatment with FG-3019 on the endpoints described in Section 3, approximately 50% of subjects will be randomized to placebo treatment (Arm B).

The placebo control is appropriate for this trial given the population of participating subjects. Enrolled subjects are those who have failed or are intolerant of approved therapies and who refuse to receive approved therapies. For these subjects the only treatment option is best supportive care, which is available to them within this protocol, and optionally experimental treatment. Therefore, placebo control, which provides for the best supportive care, is appropriate and ethical. Additionally, subjects who are randomized to placebo will be offered crossover treatment to the active arm after completion of the initial 48-week treatment period.

#### **4.3 Treatment Assignment**

Subjects are stratified by prior therapy with pirfenidone and/or nintedanib (yes/no) and randomized 1:1 to FG-3019 or placebo using an Interactive Web Response System (IWRS).

#### **4.4 Blinding**

##### **4.4.1 Rationale for Blinding**

Blinded treatment with a placebo control is the gold standard method for obtaining unbiased assessments of safety and efficacy in clinical trials of investigational drugs such as FG-3019.

##### **4.4.2 Maintenance of Blinding**

A statistician who is not otherwise affiliated with the study prepared the randomization code and the code is not available to study staff. The subjects, clinical site staff, and the FibroGen Medical Monitor and Clinical Operations staff will be blinded to whether a subject is randomized to FG-3019 or placebo. Study drug (FG-3019 or placebo) are provided in coded vials that are identified by serial number only.

##### **4.4.3 Unblinding of Treatment Assignment**

Treatment assignment of individual subjects will be unblinded during the study if this information is required to manage a SAE. Study documentation provides details on the procedures for unblinding treatment assignment by investigators. For planned assessments of efficacy, treatment assignment by groups will be unblinded but individual subject treatment assignments will not be unblinded. Treatment will be unblinded for each subject after completion of the Week 48 evaluations by unblinded FibroGen personnel. Subject eligibility for the Extended Treatment Phase will be communicated to the site.

Unblinding will also occur at the time of enrollment of subjects into the at Extended Treatment Period, after all week 48 assessments are complete **only** for designated individuals at FibroGen Inc. who are not associated with the conduct of this study. The Investigators, subjects and study teams will remain blinded till the study is complete.

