## 7 STUDY PROCEDURES-ALL COHORTS UNLESS OTHERWISE SPECIFIED

### 7.1 Study Procedures

The study procedures and assessments are presented for the Randomized Treatment phase in Appendix 1, for the Extended Treatment phase in [Appendix 2](#), and for End-of-Treatment and Follow-up periods in Appendix 3. See the Study Reference Manual for additional details.

The treatment period in the Randomized Treatment Phase begins on Day 1 (first infusion of Study Drug) and continues through Week 48. Visit windows are within  $\pm 3$  days of the scheduled visit date for Weeks 3 through 48.

After completion of Week 48 assessments and reporting of all AEs, subjects may be eligible to continue to open label treatment in the Extended Treatment Phase. All other subjects undergo the EOS assessments.

Eligible subjects from the Randomized Treatment Phase of the study are offered participation in the Extended Treatment Phase as described under Section [4.2.3](#) and illustrated in [Figure 1](#). A Transition Period of up to 3 weeks between the Week 48 Visit in the Randomized Treatment Phase and Day 1-EX in the Extended Treatment Phase is provided in order to determine subject eligibility for the Extended Treatment Phase and to arrange scheduling of the Day 1-EX Visit. The total interval between the Week 45 Visit in the Randomized Treatment Phase and the Day 1-EX Visit in the Extended Treatment Phase should not exceed 6 weeks. If necessary, an unscheduled visit should be performed to obtain repeat pulmonary function tests (FVC) if the interval between the Week 45 Visit in the Randomized Treatment Phase and the Day 1-EX Visit in the Extended Treatment Phase is expected to exceed 6 weeks.

The treatment period in the Extended Treatment Phase begins on Day 1-EX (first infusion of FG-3019) and continues until progression or withdrawal. Visit windows are within  $\pm 3$  days of the scheduled visit date.

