## 10 STATISTICS

### 10.1 Sample Size Determination

This study is planned to enroll approximately 136 subjects, which will include a target of 110 subjects who are seeking first-line therapy and 26 subjects who failed pirfenidone and/or nintedanib treatment. First-line therapy is defined as no prior therapy with pirfenidone/nintedanib or <10% relative decrease in FVC % predicted while receiving either pirfenidone or nintedanib. Failure of pirfenidone and or nintedanib treatment is defined as having  $\geq 10\%$  relative decrease in FVC % predicted during prior pirfenidone/nintedanib treatment. The effect of first-line treatment is the primary interest of the study, and is the basis for sample size determination. Assuming a 10% dropout rate and a common standard deviation of 7.3, a sample size of 55 subjects per arm in the primary analysis population provides approximately 80% power to detect a treatment difference of 4.2 in change from baseline to Week 48 in percent predicted FVC, using a two-sample t-test at the two-sided significance level of 0.05. The expected treatment difference is estimated using data from study FG-3019-049 and placebo data from published studies. In Study FG-3019-049, a mean decline of 2.8 in % predicted FVC from baseline to Week 48 was observed. The expected decline of 7.0 % predicted FVC in the placebo arm is estimated based on the weighted average of published studies ([Azuma, 2005](#), [Daniels, 2010](#), [Demedts, 2005](#), [King, Jr., 2008](#), [King, Jr., 2009](#), [King, Jr., 2011](#), [Meier-Kriesche, 2004](#), [Noble, 2011](#), [Noth, 2012](#), [Raghu, 2004](#), [Raghu, 2008](#), [Raghu, 2012](#), [Richeldi, 2011](#), [Taniguchi, 2010](#), [Zisman, 2010](#)).

Second line therapy patients are evaluated in an exploratory fashion. If the treatment effect in the pirfenidone/nintedanib failure group is similar to that in the general population, the two subgroups will be combined to achieve higher power.

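### Extension eligibility depends on the randomised arm and is sent to the site after Week 48, so the promised blind to study end cannot hold for many completers

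*Protocol*

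**What the plan says.** Protocol Section 4.4.3 limits unblinding after Week 48 to designated sponsor staff who are not associated with the conduct of the study, and then states: "The Investigators, subjects and study teams will remain blinded till the study is complete". It also says: "Subject eligibility for the Extended Treatment Phase will be communicated to the site".

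The eligibility rules differ by arm (Protocol Sections 4.2.3.1 to 4.2.3.3, repeated in SAP Part 2 Section 2.1):

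- **FG-3019, enrolled under Amendment 1 or later:** only subjects "whose FVC percent predicted value is greater than the original pre-treatment baseline" are offered the extension.
- **FG-3019, enrolled under the original protocol:** only subjects whose absolute fall from baseline is below 3 points.
- **Placebo, any version:** "All subjects assigned to Placebo (Arm B) will be offered participation in the Extended Treatment Phase for 45 weeks".

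SAP Part 2 Section 2.1 adds that substudy subjects cannot enter the extension. The one masking measure described for the extension is in Protocol Section 4.2.3: the first extension infusion lasts about 2 hours for everyone, with the stated purpose of keeping the blind.

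**The concern.** Sponsor staff hold the treatment code and pass on only the eligibility answer. That protects the blind only if the answer carries no information about the arm, and here it does. The site knows the rules because they are in the protocol. It should also know the FVC: Section 8 has the investigator act on FVC decline, and no masking of spirometry is described. Equal infusion times do nothing about this route.

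At stake are outcomes that rest on the investigator's judgement and may be made or changed after the message:

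- **Progression.** Protocol Section 10.3.4.3 counts a clinical diagnosis of IPF progression as a PFS event if it occurs during the study, and gives no Week 48 limit.
- **Respiratory-related death.** This endpoint is censored at Week 52 (Section 3.2.2), so attribution of deaths in Weeks 48 to 52 falls after the message.
- **Adverse events.** Collection runs to 4 weeks after the last dose (Section 11.3.1), with investigator-assigned causality and severity.

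Eligibility is determined as each subject finishes Week 48, whereas the data are locked only after all subjects have finished or left (Section 4.2.2). A completed subject's records can therefore still be open when the arm becomes inferable.

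**Working it through.** **Step 1. The deduction.** For a completer outside the substudy:

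| Message to site | FVC against the FG-3019 rule | What follows |
|---|---|---|
| Not eligible | not needed | FG-3019, since every placebo subject is offered the extension |
| Eligible | rule failed | placebo, since an FG-3019 subject would have been refused |
| Eligible | rule met | arm not revealed by this route |

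The contradiction needs no percentage. The remaining steps show how often it applies.

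**Step 2. Check the planning inputs.** Protocol Section 10.1 says that "a sample size of 55 subjects per arm in the primary analysis population provides approximately 80% power". Its inputs are an SD of 7.3 in both arms, 10% dropout, a 4.2-point difference and a t-test at two-sided 0.05. Evaluable subjects per arm: 55 × 0.9 = 49.5. Standard error: 7.3 × √(2/49.5) = 1.467. Then 4.2/1.467 = 2.862, and Φ(2.862 − 1.960) gives 81.7%; the noncentral t gives 80.9%. The stated power reproduces. The 4.2 is the difference between the expected mean declines of 7.0 (placebo) and 2.8 (FG-3019).

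**Step 3. Share of completers whose arm can be deduced.** The documents give no figure. Take the Week 48 change as Normal(mean, 7.3), with 1:1 allocation and equal completion. The arm is deducible when the FG-3019 rule fails.

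| Rule | FG-3019 | Placebo | Average |
|---|---|---|---|
| Amendment 1 or later: change ≤ 0 | Φ(2.8/7.3) = 64.9% | Φ(7.0/7.3) = 83.1% | 74.0% |
| Original: change ≤ −3 | Φ(−0.2/7.3) = 48.9% | Φ(4.0/7.3) = 70.8% | 59.9% |

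Under the Amendment 1 rule, the 74.0% is made up of 64.9%/2 = 32.5% told they are not eligible (FG-3019) and 83.1%/2 = 41.6% eligible without an FVC gain (placebo).

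**Step 4. Sensitivity (Amendment 1 rule unless stated; the varied inputs are assumptions).**

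- SD from 6 to 8.5: 77.9% down to 71.2%.
- 10% to 30% of completers under the original rule: 0.9 × 74.0 + 0.1 × 59.9 = 72.6%, down to 0.7 × 74.0 + 0.3 × 59.9 = 69.8%.
- Section 8 removes subjects with a confirmed decline of 10 points or more. A simulation of linear decline with measurement noise, with removal after two consecutive scheduled visits before Week 48, gives 72% to 73%.
- Extreme case, in which nobody with a Week 48 decline of 10 or more completes. The excluded shares are Φ(−7.2/7.3) = 16.2% and Φ(−3.0/7.3) = 34.1%. The result is (0.649 − 0.162 + 0.831 − 0.341)/(2 − 0.162 − 0.341) = 65.3%, or 46.4% under the original rule.

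**The case against.** Several stronger readings are tempting, and the documents do not support them.

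- **That the primary comparison is compromised.** Section 4.4.3 places unblinding after the Week 48 evaluations. A subject's Week 48 FVC, FVC category, HRCT and SGRQ are therefore measured before the message. This stands.
- **That Section 7.1 contradicts the blind by saying "subjects may be eligible to continue to open label treatment in the Extended Treatment Phase".** Everyone in the extension receives FG-3019, so current treatment can be open while the original assignment stays masked. The phrase needs no correction on this account.
- **That subjects still in the randomised phase are unblinded.** Allocation is by IWRS, the code is withheld from study staff and vials carry serial numbers only (Sections 4.3 and 4.4.2). With about 136 subjects at about 60 centres, the average is 136/60 = 2.3 per site. One completer's arm says little about another's, and spillover is not shown.
- **That adverse event data are wholly unprotected.** Section 7.1 already places reporting of all adverse events before extension entry, though it requires no lock before the eligibility message. The window is also short. Subjects who do not continue have their last visit at Week 49 (Section 4.2.2), and randomised-period events stop at the first extension infusion (SAP Part 2 Section 3.2.3).

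Two further limits stand. The randomised-period analyses are in SAP Part 1, which is not among the documents and may set a PFS cut-off. And for substudy subjects, whose number is not given, ineligibility reveals nothing.

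None of this removes the conflict within Section 4.4.3, or protects judgements that are still open when eligibility is released.

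**Conclusion.** The point holds in a limited form. The plan claims a blind to study end that its own eligibility process cannot deliver. On the planning values, about 74% of completers enrolled under Amendment 1 or later, and about 60% of those enrolled under the original protocol, would have an inferable arm. These figures assume normal changes, the planning means and SD, equal completion by arm, Week 48 FVC as the deciding value (Section 4.2.3.2 says only that it falls in the Randomized Treatment Period), and that sites see FVC. Substudy subjects are left out. A single overall figure cannot be given because the mix of protocol versions is not stated.

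The exposure is confined to investigator judgements made or edited after the message: clinical progression (unless SAP Part 1 cuts it off), attribution of respiratory deaths in Weeks 48 to 52, and adverse event causality and severity not yet final. The documents give no event counts, so the effect on those comparisons cannot be sized. The correction should be made, but it does not call the primary result into question.

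**What to change.** 1. Correct Section 4.4.3 to say that many sites and subjects can infer the original assignment once eligibility is communicated, and reconcile it with Section 4.2.3 and Sections 4.2.3.1 to 4.2.3.3.
2. Require each subject's investigator judgements through Week 48 to be entered and locked before eligibility is released: progression status and date, respiratory relatedness, and adverse event causality and severity. This extends the adverse event reporting step already in Section 7.1.
3. Keep later events, including deaths to Week 52, and label their investigator-judged attributes as not reliably blinded.
4. State that investigator-diagnosed progression counts in the blinded PFS comparison only up to release. If SAP Part 1 already sets a cut-off, refer to it.

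No dose, eligibility rule or stopping rule has to change for this. The cost is protocol wording and a data-entry deadline within the transition period of up to 3 weeks. That period must also cover eligibility determination and scheduling, with no more than 6 weeks between Week 45 and the first extension visit, so the deadline is a small but real burden.

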## 4.5 Study Treatment with FG-3019

Subjects will receive FG-3019 at a dose of 30 mg/kg by IV infusion in normal saline (unless volume is >250mL in which case the study drug can be administered undiluted) every 3 weeks. The maximum dose of FG-3019 at any infusion will be capped at 3,900 mg.

## 4.6 Concomitant Medications, Procedures and Nondrug Therapies

### 4.6.1 Concomitant Medications

Concomitant medications (any prescription and/or over-the-counter [OTC] preparation) and procedures or nondrug therapies (e.g., physical therapy, acupuncture, continuous positive airway pressure [CPAP]) used by a subject while participating in this clinical trial must be recorded from Screening Visit 1 through the End-of-Study (EOS) Visit.

Other than the restrictions that follow, concomitant medications may be given at the discretion of the Investigator. It is expected that Investigators will provide optimal medical management of idiopathic pulmonary fibrosis and that subjects may be treated with concomitant medications for their various medical conditions. Optimal medical care must be provided, and Investigators should ensure, for example, that subjects maintain stable vital signs and laboratory test values during the course of the study.

Oral prednisone or equivalent oral corticosteroid (up to 10 mg daily) and NAC (up to 1800 mg daily) will be allowed during the study.

Prohibited medications include approved or investigational agents for the treatment of interstitial lung diseases including IPF. The list of prohibited concomitant medications for treatment of IPF includes, but is not limited to, the following: sildenafil, pirfenidone, nintedanib, azathioprine, cyclophosphamide, cyclosporine, interferon gamma 1b, D penicillamine, methotrexate, leflunomide, colchicine, bosentan, ambrisentan, aminobenzoate, mycophenolate mofetil, imatinib, relaxin, etanercept, adalimumab, infliximab, anakinra, abatacept, and rituximab. If sildenafil is used for erectile dysfunction the dosage regimen should be no more than three times a week. Immunosuppressives and monoclonal antibodies used for other diseases such as rheumatoid arthritis are allowed but the indication should be clearly documented. Indications for concomitant medications should be clearly documented in the subjects clinical record (use for IPF or other diseases).

Any medications to treat IPF should be terminated within 5 half-lives of Day 1 dosing. If monoclonal antibodies are used the last dose must be at least 4 weeks before Day 1 dosing (Exclusion criterion 15).

Questions about concomitant medications should be addressed to the attention of the FibroGen Medical Monitor or designee.

